11.3. Safety Analyses

Safety data for the induction phase and the optimization/maintenance phase will be presented separately for each phase as well as for the entire treatment period (induction and optimization/maintenance phase). The baseline for safety assessments will be defined in the Statistical Analysis Plan.

Cognitive Function

Computerized cognitive test battery and HVLT-R: Descriptive statistics of each of the cognitive domain scores and changes from baseline will be provided at each scheduled time point.

Adverse Events

The verbatim terms used in the CRF by investigators to identify adverse events will be coded using the Medical Dictionary for Regulatory Activities (MedDRA). Treatment-emergent adverse events are adverse events with onset during the treatment phase or that are a consequence of a pre-existing condition that has worsened since baseline. All reported adverse events with onset during the treatment phase (ie, TEAEs, and adverse events that have worsened since baseline) will be included in the analysis. For each adverse event, the percentage of subjects who experience at least 1 occurrence of the given event will be summarized.

Treatment emergent AEs of special interest will be examined separately grouped in the following categories: drug abuse, dependence and withdrawal, increased blood pressure, increased heart rate, transient dizziness/vertigo, impaired cognition, cystitis, anxiety, events potentially related to suicidality, hepatic adverse events, events related to renal disorders, and symptoms of dissociation persisting beyond the typical ≤ 2 hour post esketamine administration, as well as delirium, psychosis or mania.

Summaries, listings, datasets, or subject narratives may be provided, as appropriate, for those subjects who die, who discontinue treatment due to an adverse event, or who experience a severe or a serious adverse event.

Vital Signs

Descriptive statistics of body weight, temperature, pulse/heart rate, respiratory rate, pulse oximetry and supine blood pressure (systolic and diastolic) values and changes from baseline will be provided at each scheduled time point. Any treatment-emergent abnormalities will be listed.

Clinical Laboratory Tests

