12.3.2. Serious Adverse Events

All SAEs, as well as PQC, occurring during the study must be reported to the appropriate sponsor contact person by study-site personnel within 24 hours of their knowledge of the event.

Serious adverse events, including those spontaneously reported to the investigator within 30 days after the last dose of study drug, must be reported using the Serious Adverse Event Form. The sponsor will evaluate any safety information that is spontaneously reported by an investigator beyond the time frame specified in the protocol.

Information regarding serious adverse events will be transmitted to the sponsor using the Serious Adverse Event Form, which must be completed and signed by a physician from the study site, and transmitted to the sponsor within 24 hours. The initial and follow-up reports of a serious adverse event should be made by facsimile (fax).

All serious adverse events that have not resolved by the end of the study, or that have not resolved upon discontinuation of the subject's participation in the study, must be followed until any of the following occurs:

- The event resolves
- The event stabilizes
- The event returns to baseline, if a baseline value/status is available
- The event can be attributed to agents other than the study drug or to factors unrelated to study conduct
- It becomes unlikely that any additional information can be obtained (subject or health care practitioner refusal to provide additional information, lost to follow-up after demonstration of due diligence with follow-up efforts)

Suspected transmission of an infectious agent by a medicinal product will be reported as a serious adverse event. Any event requiring hospitalization (or prolongation of hospitalization) that occurs

during the course of a subject's participation in a study must be reported as a serious adverse event, except hospitalizations for the following:

- Hospitalizations not intended to treat an acute illness or adverse event (eg, social reasons such as pending placement in long-term care facility)

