1.2. Trial Design

This is a multicenter, open-label long term extension study to evaluate the safety, tolerability, and efficacy of intranasal esketamine in subjects with TRD. The study population will include adult and elderly men and women who previously participated in studies ESKETINTRD3001, ESKETINTRD3002, ESKETINTRD3003, ESKETINTRD3004, ESKETINTRD3005, or ESKETINTRD3006 (US sites only) and will have met the inclusion/exclusion criteria for entry into those prior studies.

For subjects who participated in studies ESKETINTRD3003, ESKETINTRD3004, ESKETINTRD3005 or ESKETINTRD3006 (US sites only) and have responded to intranasal esketamine treatment, it is considered an ethical obligation to provide continued intranasal esketamine treatment if the benefit/risk profile was favorable for the subject at the time of completion of the previous study. Subjects in the placebo-controlled, double blind ESKETINTRD3005 and who are non-responders at the end of the induction phase were eligible to enter the open label induction phase of ESKETINTRD3004, therefore if enrollment in the ESKETINTRD3004 had completed these subjects were given the opportunity to enter this study, if clinically appropriate. For subjects who completed the induction phase and 6-month follow up phase of the ESKETINTRD3001 or ESKETINTRD3002 study, this study provided an opportunity for subjects to have an induction phase with open-label intranasal esketamine.

An Independent Data Monitoring Committee (IDMC) is commissioned for this study to review safety data periodically.

This study (54135419TRD3008) has 2 open label phases:

- A 4-week induction phase (if applicable)
- A variable duration optimization/maintenance phase

The duration that a subject may participate in the study is variable and is based on the subject's point of entry into the study and the timing of when the predefined criteria (below) for ending study participation occurs.

Study participation will be stopped:

- At the time intranasal esketamine is commercially available or a pre-approval access program is available to the subject in the subject's respective country; or
- The subject no longer benefits from further treatment (based on the investigator's clinical judgment), or withdraws consent; or
- The company terminates clinical development of intranasal esketamine for TRD.

Subjects will have a final study visit within 1 week of the last dose of intranasal esketamine.

A description of the study phases is provided below.

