2.1.2. Analysis Phase Start and End Dates

Induction Phase

The start date of the induction phase (referred to as, 'IND start date') is the date of the first dose of intranasal study medication in the induction phase. For subjects who continue to the optimization/maintenance phase, the induction phase end date (referred to as, 'IND end date') is the date of first dose of intranasal study medication taken in the optimization/maintenance phase or the date of the last visit in the induction phase if date of the first dose is missing. For subjects who discontinue in the induction phase, IND end date is the maximum of the date of the last visit in the induction phase or the date of early termination from the induction phase.

The start date/time of the induction phase (referred to as, 'IND start date/time') is the IND start date and the time of the first dose of intranasal study medication in this phase. If no intranasal study medication is administered, the time will be left blank.

The start and end dates for the induction phase are only defined for subjects who enter the study at the induction phase.

Optimization/Maintenance Phase

The start date of the optimization/maintenance phase (referred to as, 'OP/MA start date') is the OP/MA start date of the first dose of intranasal study medication in this phase. For subjects who complete/discontinue from the optimization/maintenance phase, the phase end date (referred to as, 'OP/MA end date') is the maximum of the date of the last visit in the optimization/maintenance phase or the date of completion/withdrawal from the optimization/maintenance phase.

The start date/time of the optimization/maintenance phase (referred to as, 'OP/MA start date/time') is the OP/MA start date and the time of the first dose of intranasal study medication in this phase.

Follow-Up Phase

The start date of the follow-up (post-treatment) phase (referred to as, 'F/U start date') is the day after the end date of the last treatment phase in which the subject participated. For subjects who complete/discontinue from the follow-up phase, the follow-up phase end date (referred to as, 'F/U end date') is the maximum of the last follow-up visit date or end of trial date.

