2.6. Imputation Rules for Missing Adverse Event (AE) Dates

Treatment-emergent adverse events (TEAEs)

- For subjects who enter the study at the induction phase, treatment-emergent AEs are those events with an onset date/time on or after the start of IND phase study medication, and occurred on or before the end of the optimization/maintenance phase. A conservative approach will be used to handle the missing dates for AEs
- For subjects who directly enter the optimization/maintenance phase of this study, treatment-emergent AEs are those events with an onset date/time on or after the start of OP/MA phase study medication, and occurred on or before the end of the optimization/maintenance phase. A conservative approach will be used to handle the missing dates for AEs

Onset Date

AEs for each phase are those events with an onset date/time on or after the start of that particular phase and occurred on or before the end of that phase. The rules for estimating incomplete AE onset dates will be as follows:

Subject Entry into 54135419TRD3008 at the IND Phase:

If the onset date of an adverse event is missing the day only, it will be set to:

- i) First day of the month that the AE occurred, if month/year of the onset of AE is different than the month/year of IND start date
- ii) The day of IND start date, if the month/year of the onset of AE is the same as month/year of the IND start date and month/year of the AE resolution date is different
- iii) The day of IND start date or day of AE resolution date, whichever is earliest, if month/year of the onset of AE and month/year of the IND start date and month/year of the AE resolution date are the same.

If the onset date of an adverse event is missing both day and month, it will be set to the earliest of:

- i) January 1 of the year of onset, as long as this date is after the IND start date
- ii) One day after the IND start date, if this date is the same year that the AE occurred.

A completely missing onset date of an adverse event will be set to the IND start date.

Subject Entry into 54135419TRD3008 at the OP/MA Phase:

If the onset date of an adverse event is missing day only, it will be set to:

- i) First day of the month that the AE occurred, if month/year of the onset of AE is different than the month/year of OP/MA start date
- ii) The day of OP/MA start date, if the month/year of the onset of AE is the same as month/year of the OP/MA start date and month/year of the AE resolution date is different

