6.1. Adverse Events

The Medical Dictionary for Regulatory Activities (MedDRA) (version 18.1 or above) will be used to classify AEs by system organ class and preferred term. TEAEs that occurred in each study phase will be summarized by system organ class and preferred term.

The number (%) of subjects with TEAEs, serious TEAEs (SAEs), and TEAEs that led to study drug discontinuation will be summarized by system organ class and preferred term. Data listings will be generated for deaths, other SAEs, and discontinuations due to AEs.

In addition, data listing and summary will be provided for subjects with AEs ongoing at the time of entry into this study.

A TEAE is an event that is new in onset or increased in severity following treatment initiation. An event that starts prior to, and ends after the initiation of study medication will be considered treatment-emergent only if the severity increases after the start of medication.

Treatment-emergent adverse events (TEAEs) are defined as follows for each study phase:

- TEAEs in the induction phase:
 - a. If AE onset time is not missing:
 - i) If subjects continue to OP/MA phase: IND phase start date/time \leq AE onset date and time $<$ IND phase end date
 - ii) If subjects discontinue in the IND phase: IND phase start date/time \leq AE onset date and time \leq IND phase end date

-
- b. If AE onset time is missing:
 - i) If subjects continue to OP/MA phase: IND phase start date/time \leq AE onset date $<$ IND phase end date
 - ii) If subjects discontinue in the IND phase: IND phase start date/time \leq AE onset date \leq IND phase end date
 - TEAEs in the optimization/maintenance phase:
 - a. If AE onset time is not missing: OP/MA phase start date/time \leq AE onset date and time \leq OP/MA phase end date
 - b. If AE onset time is missing: OP/MA phase start date \leq AE onset date \leq OP/MA phase end date
 - For the AEs that have both day and month missing, treatment-emergent flag is assigned based on the rules presented in Section 2.6.

In addition, TEAEs will be summarized by severity and relationship to study medication using the preferred term. For the summaries of TEAEs by severity/relationship to study medication, the observation with the most severe occurrence/closest relationship to study medication will be chosen if there is more than one incident of an AE reported during the analysis phase by the subject. AE duration for transient dizziness/vertigo and anxiety will also be summarized.

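### Deaths and serious adverse events with onset after phase end, but within 30 days of the last dose, are listed but enter no SAP incidence table

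*SAP*

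**What the plan says.** **Window for counting.** For subjects entering at induction, SAP 2.6 states that "treatment-emergent AEs are those events with an onset date/time on or after the start of IND phase study medication". The sentence then closes the window with the words "and occurred on or before the end of the optimization/maintenance phase". Direct entrants to the optimization/maintenance phase have the same rule, starting at their first dose in that phase. SAP 2.1.2 sets that phase's end date: it "is the maximum of the date of the last visit in the optimization/maintenance phase or the date of completion/withdrawal from the optimization/maintenance phase". No days are added after the last dose. The final visit is close to the last dose: "Subjects will have a final study visit within 1 week of the last dose of intranasal esketamine" (SAP 1.2).

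**What is tabulated.** SAP 6.1 gives numbers and percentages for treatment-emergent events, serious treatment-emergent events and those leading to discontinuation. The special-interest categories, including suicidality, are likewise limited to treatment-emergent events. Deaths and other serious events are also listed, with no stated restriction to treatment-emergent ones.

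**What is collected.** Protocol 12.3.2: "Serious adverse events, including those spontaneously reported to the investigator within 30 days after the last dose of study drug, must be reported". The synopsis (Safety Analysis) says that subjects who die or have a serious event will be summarised separately. Protocol 11.3 says only that summaries, listings or narratives may be provided.

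**French follow-up.** SAP 2.4.3 says the Follow-up analysis set will be used to summarise all safety evaluations in that phase. SAP 6.1 puts French follow-up adverse events in a listing.

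**Worsening events.** SAP 6.1 says an event that starts before and continues past first dose "will be considered treatment-emergent only if the severity increases after the start of medication". Protocol 11.3 also includes events "or that are a consequence of a pre-existing condition that has worsened since baseline". The phase-level inequalities that follow in SAP 6.1, and the rule in SAP 2.6, test onset only.

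**The concern.** Safety is the primary objective, with effects on suicidal ideation and behaviour named in it. The protocol asks for serious events up to 30 days after the last dose, but the SAP's percentages stop at phase end. A reader of the serious-event or suicidality table would not know that later events exist unless they also worked through the listings. The C-SSRS does not fill the gap, because its last scheduled administration is the Early Withdrawal/End of Study visit.

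The cut-off also treats equal intervals from a dose unequally. Sessions may be 4 weeks apart in this phase. A serious event 20 days after a dose counts if the subject remains in the phase. The same event 20 days after a final dose does not count once the phase has closed.

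The worsening rule raises a separate question of consistency: a programmer who implements the inequalities literally may drop events that the text just above them includes.

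**Working it through.** The plan states no figure to reproduce, so the check applies its date rules.

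**Inputs**
- Serious event reporting window: 30 days after the last dose (Protocol 12.3.2).
- Final visit: 0 to 7 days after the last dose (SAP 1.2).
- Phase end: the later of the last visit and the completion/withdrawal date (SAP 2.1.2).

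**Days of the reporting window that fall after the cut-off**

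Days not covered = 30 − (phase end − last dose), with a floor of 0.

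| Phase end, days after last dose | Calculation | Days not covered | Share of 30 |
|---|---|---|---|
| 0 | 30 − 0 | 30 | 100% |
| 3 | 30 − 3 | 27 | 90% |
| 7 | 30 − 7 | 23 | 77% |

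These rows assume that completion or withdrawal is dated no later than the final visit. A later date shortens the gap. As an illustration, a withdrawal dated 28 days after the last dose leaves 30 − 28 = 2 days.

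**Test events, with the phase ending 7 days after the last dose**

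| Event | Onset rule (SAP 2.6 and the 6.1 inequalities) | SAP 6.1 text on severity |
|---|---|---|
| Onset at last dose + 5 | counted | counted |
| Onset at last dose + 15 | not counted | not counted |
| Onset at last dose + 30 | not counted | not counted |
| Ongoing at entry, worsens on day 50, original onset date kept | not counted | counted |
| Same worsening entered as a new record with onset on day 50 | counted | counted |

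The rule turns on onset, not on the date of the report. An event with onset during treatment that is reported late is still counted.

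The +15 and +30 rows are the main gap: neither rule in the SAP admits them. The fourth row is the secondary point, and it is the only case in which the two rules disagree.

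**The case against.** There is a serious case on the other side.

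- **The events are not hidden.** Deaths and other serious events are listed without a treatment-emergent restriction. This stands: a reader might infer that such events vanish from the report, and the documents do not support that.
- **The cut-off is not simply the last visit.** SAP 2.1.2 takes a later completion or withdrawal date if there is one. Subjects who miss visits are contacted weekly, up to 4 times, before discontinuation (Protocol 9.1.3 and 10.2), so withdrawal can fall weeks after the last dose. This stands and limits the 23-to-30-day figure to its stated assumption.
- **Collection after the last visit is largely passive.** Protocol 12.3.1 takes adverse events up to the last study-related procedure, and 12.3.2 then relies on spontaneous reports. A percentage over the whole cohort would be under-ascertained. This argues for a separate, labelled row. It does not argue against any count.
- **Some completers may go on to commercial drug.** Participation ends when esketamine is approved and accessible locally, so the 30 days after the last study dose need not be drug-free. This stands as a caution on interpretation.
- **Worsened events are already treatment-emergent.** The SAP 6.1 text and Protocol 11.3 say so, and SAP 6.1 plans a listing and summary of events ongoing at entry. Protocol 12.1.1 also treats an aggravation as an adverse event, so it may be recorded with its own onset date. The tempting reading that worsened events enter no incidence table is therefore wrong. What survives is that the inequalities, introduced as the definition for each phase, omit the severity condition.
- **The study is single-arm with no hypothesis.** No test or decision rule changes. That is true, but describing safety is the purpose of the study.

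**Conclusion.** The main point holds in a limited form. Deaths and serious events with onset after phase end but within 30 days of the last dose are in no SAP incidence table and in no suicidality percentage, which sits badly with the protocol synopsis. Between 23 and 30 of the 30 days are affected if completion or withdrawal is dated no later than a final visit 0 to 7 days after the last dose; fewer days are affected if it is dated later. SAP 2.4.3 and 6.1 also disagree on whether French follow-up adverse events are summarised or only listed.

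The worsening issue is a drafting inconsistency. It loses an event only if the record keeps its original onset date and the inequalities are programmed literally. The documents do not give the recording convention.

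A reader might also infer that suicidality is known to rise in the weeks after stopping, that many subjects enter with ongoing events, or that incidence is materially understated. The documents give no figures for any of these, and the point does not depend on them.

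**What to change.** 1. In SAP 6.1, beside the on-treatment table, add one summary of deaths, serious events and suicidality-category events with onset from first dose to last dose + 30 days, or to phase end if later. Label it as resting partly on spontaneous reports after the last visit, and note that some completers may have continued on commercial drug.
2. Reconcile SAP 2.4.3 with SAP 6.1 on whether French follow-up adverse events are summarised or only listed.
3. Add to the rules in SAP 2.6 and the phase inequalities in SAP 6.1 that an event with onset before the start also qualifies if its severity increases on or after the start, using the date of the increase. State how a worsening is recorded.

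The cost is SAP wording, one table and one derived flag. The summary uses reports that the protocol already requires, and no visit or clinical procedure changes. The drawback is incomplete ascertainment after the last visit, which the label discloses.

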2.7. Imputation Rules for Missing Concomitant Medication Dates

If a partial date is reported, it is assumed the medication (or therapy) was taken in all phases that overlap with the partial date. If both start and end dates are missing but this concomitant medication was taken both prior to the study entry and still ongoing at study end, it is assumed medication was taken in all phases.

The rules for estimating an incomplete concomitant medication start date are as follows:

Subject Entered into 54135419TRD3008 at the IND Phase:

If the month of the concomitant medication start date is equal to the month of the start of the induction phase, then the estimated start date is the IND start date;

If the month of the concomitant medication start date is greater than the month of the start of the induction phase and earlier than the study end date, then the estimated start date of the concomitant medication is the first day of the month;

If the month of the concomitant medication start date is greater than the month of the study end date, then no imputation will be done;

If the month and year of the concomitant medication start date are known and the IND start date is after the month of the concomitant medication start date, then no imputation will be done;

If either the month or year of the concomitant medication start date is missing, no imputation is to be performed.

Subject Entered into 54135419TRD3008 at the OP/MA Phase:

If the month of the concomitant medication start date is equal to the month of the start of the optimization phase, then the estimated start date is the OP/MA start date;

If the month of the concomitant medication start date is greater than the month of the start of the OP/MA phase and earlier than the study end date, then the estimated start date of the concomitant medication is the first day of the month;

If the month of the concomitant medication start date is greater than the month of the study end date, then no imputation will be done;

If the month and year of the concomitant medication start date are known and the OP/MA start date is after the month of the concomitant medication start date, then no imputation will be done;

If either the month or year of the concomitant medication start date is missing, no imputation is to be performed.

